7.2 STUDY SCHEDULE

The complete schedule for study visits is detailed below and summarized in the subsequent Study Flow Diagram (**Figure 7.3a**) and Table of Study Visits (see below Schedule of Events, **Table 7.3a**).

In the event of an emergency that disrupts patient or institutional access and usual study care, such as an unexpected disaster or pandemic, refer to **Protocol Section 17.0 (EMERGENCY DISASTER/ PANDEMIC MANAGEMENT PLAN)** for allowable adjustments to the study procedures and schedule that may be invoked as dictated by the nature of the emergency.

7.2.1 Screening Visits (Study Day -90 through 0; Screening Visit #1&2)

In order to be eligible for randomization, patients must proceed through a series of screening steps. At Screening Visit #1, a preliminary evaluation is performed and if eligibility criteria are met the patient will proceed to the screening HRCT scan (Screening Visit #2) to assess for the presence of any ground glass opacity and to exclude concurrent findings of concern that may require additional evaluation or exclude the patient from further participation. If all inclusion and exclusion criteria are met, the patient will proceed to the baseline evaluation where a final check of pulmonary function and pregnancy testing is required to meet randomization criteria:

7.2.1.1 **Screening Visit #1.** (preferably within 60 d, but no earlier than 90 d prior to randomization)

- Patient provides written informed consent and research HIPAA authorization prior to any evaluation or testing.

- b. A review of existing medical records and tests, provided by the patient or referring physician, is performed to document the history of scleroderma and general medical history.
- c. Vital signs obtained.
- d. The patient undergoes a complete medical history and physical examination.
- e. Review of concomitant medications including all medications taken within past 3 months and any prior use of medications detailed in Section 7.5.1 (Prohibited Medications & Treatments with Potential Disease Modifying Effects).
- f. Pulmonary function testing for spirometry and diffusing capacity will be completed unless acceptable testing has been completed within 30 days of the screening visit and approved in advance by the Pulmonary Function Core at UCLA.
- g. A limited subset of the UCLA SCTC GIT questionnaire (including only Questions #1-8) is completed by the participant
- h. The patient has blood drawn for monitoring blood tests and serum pregnancy test (if applicable).

7.2.1.2 **Screening Visit #2.** (may not be completed until results from screening visit #1 confirm potential eligibility, must be completed within 60 days of randomization)

- a) Thoracic HRCT with visual review for the presence of entry and exclusion criteria and with Quantitative Image Analysis

7.2.2 Enrollment/Baseline Visit (Study Day 0; Visit #1)

Subjects who meet all defined inclusion and exclusion criteria (up to this point) will be asked to return for the baseline visit. This will preferably occur within 60 days of their initial screening evaluation, but must occur within 90 days of their initial evaluation. For subjects who have not met study enrollment criteria, their participation will end and they will not proceed. The following studies will take place at the baseline visit.

- a) A focused interval history and examination will be performed.
- b) Vital signs obtained.
- c) Review of concomitant medications
- d) Pulmonary function testing for spirometry and diffusing capacity will be completed.
- e) Urine pregnancy test performed (if indicated)
- f) Patient Reported Outcomes (PROs) in the form of patient responses to standardized patient questionnaires (SGRQ; SHAQ; PROMIS-29; UCLA SCTC GIT; LCQ).
- g) Complete the Mahler Baseline Dyspnea Index.
- h) An assessment of skin thickness and function scores (mRSS)
- i) Patient and Physician Global Assessments (no transition questions)
- j) Blood collection for the Biological Specimen Repository

If the repeat FVC-% fails to be within 10% of the value obtained at screening or is not > 45% and ≤ 85%, the subject will be offered one opportunity to repeat testing within 7 days. If they choose not to repeat testing or if the repeat testing remains outside of the required range, their participation in the study will end.

If the subject meets the repeat FVC-% inclusion criteria, and assuming that pregnancy testing is negative if required, the site coordinator will complete the online eligibility case report form and login to the electronic web-based randomization application to randomize the participant.

Once randomization has occurred, the UCLA Pharmacy Core or the designated site Pharmacy, will confirm the drug and bottle assignment. In conjunction with a prescription signed by the Clinical Site

investigator, study drugs will be dispensed according to established protocol. Randomization will occur via the Data Coordinating Center and result in a notification of study assignment group to the UCLA Pharmacy Core and the Site Pharmacy. Study drug (PFD/Plac) will be released in a double-blinded manner and neither the study investigators or staff, or the patient, will know the treatment assignment.

7.2.3 Follow-up Visits (Months 0.5-18, Study Visits #2-21)

There are a number of potential side effects of the study drugs that may be detected only through regular follow-up and blood testing monitoring. Given the nature of the study drugs, good clinical practice will require study visits for the purpose of monitoring every month for the first 6 months and every 3 months thereafter until drug therapy is completed at month 18. In addition to this clinical monitoring, outcome assessments are scheduled to occur every 3 to 6 months throughout the duration of the study. Finally, additional contact will be maintained with the subjects through regularly scheduled phone contacts to assure that drug titration and dosing, changes in health and adverse events are adequately tracked and recorded.

7.2.3.1 Regular Follow-up Visits (Months 1 through 18; Visits 3, 5-9, 12, 15, 18, 21).

Regular follow-up visits include a combination of toxicity monitoring and outcome assessments. Not all assessments are performed at each visit. Therefore, after each task listed below, a list of visit numbers (and corresponding month on study drug) is included to indicate when the task will be performed. Each visit must be completed within a specified time window with respect to the protocol defined follow-up date: Visit #3 = ± 7 d; Visits #5-9 and 12 = ± 10 d; Visit #15, 18, 21 = ± 14 d.

- a) A focused interval history and examination will be performed.
[Visit # 3 (month 1), 5-9 (months 2-6), 12 (month 9), 18 (month 15), 21 (month 18)]
- b) Vital signs obtained.
[Visit # 3 (month 1), 5-9 (months 2-6), 12 (month 9), 15 (month 12), 18 (month 15), 21 (month 18)]
- c) Assessment of adverse events
[Visit # 3 (month 1), 5-9 (months 2-6), 12 (month 9), 15 (month 12), 18 (month 15), 21 (month 18)]
- d) Review of concomitant medications
- e) Study drug reconciliation
[Visit # 3 (month 1), 5-9 (months 2-6), 12 (month 9), 15 (month 12), 18 (month 15), 21 (month 18)]
- f) Study drug dispensing
[Visit # 3 (month 1), 5-9 (months 2-6), 12 (month 9), 15 (month 12), 18 (month 15), 21 (month 18)]
- g) Toxicity monitoring with blood tests.
[Visit # 3 (month 1), 5-9 (months 2-6), 12 (month 9), 15 (month 12), 18 (month 15), 21 (month 18)]
- h) Urine pregnancy test performed (if indicated)
[Visit # 3 (month 1), 5-9 (months 2-6), 12 (month 9), 15 (month 12), 18 (month 15), 21 (month 18)]
- i) Pulmonary function testing for spirometry and diffusing capacity will be completed.
[Visit #6 (month 3), 9 (months 6), 12 (month 9), 15 (month 12), 18 (month 15), 21 (month 18)]

- j) Patient Reported Outcomes (PROs) in the form of patient responses to standardized patient questionnaires
 - SGRQ
 - [Visit #6 (month 3), 9 (month 6), 12 (month 9), 15 (month 12), 18 (month 15), 21 (month 18)]
 - SHAQ; PROMIS-29; UCLA SCTC GIT; CRISS; LCQ
 - [Visit #9 (month 6), 15 (month 12), 21 (month 18)]
- k) Complete the Mahler Transitional Dyspnea Index.
 - [Visit #6 (month 3), 9 (months 6), 12 (month 9), 15 (month 12), 18 (month 15), 21 (month 18)]
- l) An assessment of skin thickness and function scores (mRSS)
 - [Visit #6 (month 3), 9 (months 6), 12 (month 9), 15 (month 12), 18 (month 15), 21 (month 18)]
- m) Physician and Patient Global Assessments.
 - [Visit #9 (month 6), 15 (month 12), 21 (month 18)]

7.2.3.2 Additional Assessments at the 12-Month & 18 Month Visit (Visit #15 and 21).

- a) In addition to testing completed at the Regular Follow-up Visits described above, the following will take place at the 12 Month Visit:
 - Blood collection for the Biological Specimen Repository
 - The patient undergoes a complete medical history and physical examination.
- b) In addition to testing completed at the Regular Follow-up Visits described above, the following will take place at the 18 Month Visit:
 - Blood collection for the Biological Specimen Repository
 - Thoracic HRCT with Quantitative Image Analysis

7.2.3.3 Phone Follow-up Visits.

Month 0.5 (Visit #2); Month 1.5 (Visit #4); Months 7-8 (Visit #10-11); Months 10-11 (Visit #13-14); Months 13-14 (Visit #16-17); Months 16-17 (Visits 19-20)
(Visit windows ± 7 d for Visits 2 & 4; ± 10 d for all others)

- a) Focused interval history
- b) Assessment of adverse events
- c) Review of Concomitant medications
- d) Study drug reconciliation (focused review of current dose and changes since last visit, missed doses, remaining supply)

7.2.4 Final Phone Follow-up Visit / Early Termination Final Phone Visit

Month 19 (Visit #22) or within 30 days of completely withdrawing from study

(Visit window ± 10 d)

- a) Focused interval history
- b) Assessment of adverse events
- c) Review of medications and alternative treatments (if premature termination visit)
- d) Reasons for leaving study (if premature termination visit)

7.2.5 Follow-up for Participants who Prematurely Discontinue Study Drug Treatment or who Completely Withdraw from the Study

Should a participant prematurely discontinue all study drugs he/she will be asked to return for the key outcome determinations at 12 and 18 months, as detailed above. In addition, at that time, any medication prescribed by their treating physician since discontinuing study drugs will be recorded.

The participant will also be asked to participate in an exit visit as detailed in 7.2.4 above. Should the participant die, the cause of death will be determined and recorded if possible.

In the event that one study drug is permanently discontinued due to tolerability, adverse event or other medical consideration, then continued use of the remaining study drug will be according to the following pre-specified management:

- If only PFD/Plac is permanently discontinued, the participant may continue to take MMF according to the protocol and continue their participation in all study visits according to the normal protocol-defined schedule of events.
- If MMF is prematurely discontinued, the participant must stop the PFD/Plac study medication as well and will be asked to return for key outcome determinations at 12 and 18 months as detailed in Section 5.3.3 (Handling of Premature Participant Withdrawals)

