--	--

	
unless the patient is on MMF and the responsible physician indicates that continued use is in the best clinical interest of the patient.
 
17. Active infection (lung, ulcers or elsewhere) whose management would be compromised by immunosuppression.
 
18. Other serious concomitant medical illness (e.g., active malignancy within the past 5 years other than surgically-removed local skin cancer such as a basal cell carcinoma), chronic debilitating illness (other than SSc), unreliability or drug abuse that might compromise the patient's participation in the trial.
 
19. Current use, or use within the 30 days prior to their baseline visit, of prednisone (or equivalent) in doses >10 mg/day.
 
20. Smoking of cigars, pipes, or cigarettes during the past 6 months.
 
21. Use of contraindicated medications, including medications with putative disease-modifying properties that do not meet the exposure limits described in Exclusion Criteria #15 and #16, moderate or strong inhibitors of cytochrome P450 (CYP) isozyme 1A2 (CYP1A2) (note ciprofloxacin allowed up to a dose of 500 mg twice daily), and moderate inducers of CYP1A2 (such as tobacco smoke, or phenytoin). See Section 7.5 for complete list.

--	--

SUMMARY SCHEMATIC OF STUDY DESIGN

SUMMARY TABLE OF STUDY VISITS AND ASSESSMENTS**

	Screen		Randomized Double-blind Phase																				Exit visit*	
	S1	S2	V1	V2	V3	V4	V5	V6	V7	V8	V9	V10	V11	V12	V13	V14	V15	V16	V17	V18	V19	V20	V21	
Visit #	Sc-1	Sc-2	0	0.5 (14 days) ±7d	1 (28 days) ±7d	1.5 (42 days) ±7d	2 (56 days) ±10d	3 (84 days) ±10d	4 (112 days) ±10d	5 (140 days) ±10d	6 (168 days) ±10d	7 (196 days) ±10d	8 (224 days) ±10d	9 (252 days) ±10d	10 (280 days) ±10d	11 (308 days) ±10d	12 (336 days) ±10d	13 (364 days) ±10d	14 (392 days) ±14d	15 (420 days) ±10d	16 (448 days) ±10d	17 (476 days) ±10d	18 (504 days) ±14d	V22
Month on Study (Month = 28 days)																								Month 19 (532 days) ±10d
Phone contact					X		X						X	X		X	X		X	X		X	X	X
On-Site Visit	X	X	X		X		X	X	X	X	X		X				X		X		X		X	
Complete H&P	X																							
F/u SSc-H&P			X		X		X	X	X	X	X		X											
Vital signs	X		X		X	X	X	X	X	X	X		X			X		X		X		X		
mRSS			X				X				X			X			X			X			X	
Study Consent	X																							
Adverse events			X	X	X	X	X	X	X	X	X	X	X	X	X	X	X	X	X	X	X	X	X	
Concomitant Medications	X		X	X	X	X	X	X	X	X	X	X	X	X	X	X	X	X	X	X	X	X	X	
Dispense meds			X		X	X	X	X	X	X	X			X			X			X				
Drug reconciliation			X		X	X	X	X	X	X	X			X			X			X			X	

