8.1.1 Definition of Adverse Events (AEs)

Adverse event means any untoward medical occurrence, such as an abnormal laboratory finding, physical sign, symptom, or diagnosis of a disease state, that is temporally associated with the use of an interventional treatment or procedure in a human subject regardless of whether or not it is considered intervention-related [consistent with 21 CFR 312.32 (a)].

8.1.1.1 Treatment-emergent AEs (TEAEs):

TEAEs are those that start or worsen after the start of study treatment and up to 7 days (for AEs) and 30 days (for serious AEs) after the last dose of study treatment. This AE definition would include the following:

- Any pre-existing condition that increases in severity or changes in nature during or as a consequence of the study treatment administration
- Complications resulting from protocol-mandated procedures
- AEs occurring as a result of product withdrawal, abuse or overdose
- A change in a laboratory variable if considered by the investigator to be clinically significant or if it is caused (or should have caused) the investigator to reduce or discontinue the use of the product or initiate a non-protocol therapy or procedure

8.1.1.2 AEs of Special Interest:

AEs of Special Interest represent a specific subset of all AEs and are defined by the study protocol based on two distinct features: 1) their likely association with the investigational drug(s), and 2) the presence of pre-specified study drug management guidelines that are to be followed when the AE occurs.

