8.3.2 Serious Adverse Event Reporting

All SAEs will be mapped to system organ classes (SOC) using preferred MedDRA SOC terms, graded for severity and relationship to study drugs as detailed above, and recorded with start dates occurring any time after informed consent is obtained until 30 days after the last day of study participation. At each study visit, the investigator will inquire about the occurrence of SAEs since the last visit and study participants and their significant others will be asked in advance to notify the study investigators immediately regarding any hospitalization, serious change in their health or in the event of a death. Events will be followed for outcome information until resolution or stabilization, with stop dates recorded for resolution.

Regardless of whether the SAE is deemed related to use of the study agents, the data for the SAE must be reported with the appropriate information by the study investigators or their designee to the Data Coordinating Center within 24 hours of learning of the event. In addition, new follow-up data must be reported within 24 hours of receipt. The designated study medical monitor or designee may be contacted at any time for immediate discussion regarding such an event.

Hospitalizations for the following reason, which are not related to an AE, do not require reporting:

- Hospitalization or prolonged hospitalization for diagnostic or elective surgical procedures for preexisting conditions.

Deaths occurring in patients who have withdrawn from the active treatment phase of the study will not be considered SAEs if the death occurs more than 30 days after last dose of study treatment. When recording a death, the event or condition that caused or contributed to the fatal outcome

should be reported as the single medical concept. If the cause of death is unknown and cannot be ascertained at the time of reporting, the report will be identified as an “Unexplained Death”.

Investigators must report all SAEs to their governing IRB/IEC, as required by local regulations and guidelines.

A record of all SAEs, by study subject and preferred SOC terms will be recorded centrally by the DCC.

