8.3.4 Reporting of Pregnancy

- a) Pregnancies should be reported from the time the patient signs the informed consent until 30 days after the last dose of study drug. Study treatment must be immediately discontinued if a patient becomes pregnant. Although pregnancy is not considered an SAE, a report should be completed and expeditiously submitted to the DCC and to Genentech, Inc. Follow-up to obtain the outcome of the pregnancy should also occur. Abortion, whether accidental, therapeutic, or spontaneous, should always be classified as serious, and expeditiously reported as an SAE. Similarly, any congenital anomaly/birth defect in a child born to a female subject exposed to the study drug should be reported as an SAE.

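### The final safety call (Visit 22) is fixed to study day 532 rather than to the last dose, so scheduled enquiry does not reliably cover the 30-day window for serious adverse events and pregnancies

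*Protocol*

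**What the plan says.** **Timing of the call.** Protocol Section 7.2.4 places the last phone contact at "Month 19 (Visit #22) or within 30 days of completely withdrawing from study", with a window of ±10 days. The Summary Table of Study Visits and Assessments uses a 28-day month and puts Visit 22 at day 532 ±10. It lists Visit 21, when drug therapy is due to be complete, as "18 (504 days) ±14d". Section 7.2.3.1 confirms that window: "Visit #15, 18, 21 = ± 14 d". The footnote to the table gives early leavers an exit contact within 30 days, also with ±10 days attached, of early termination or withdrawal.

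**Intervals to be covered.** These are counted from different starting points:

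- Protocol Section 8.1.1.1 and SAP Section 11.2.1 count treatment-emergent events "up to 7 days (for AEs) and 30 days (for serious AEs) after the last dose of study treatment".
- Protocol Section 8.3.4 makes pregnancies reportable "until 30 days after the last dose of study drug".
- Protocol Section 8.3.2 records SAEs "until 30 days after the last day of study participation".

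**Content of the call.** Section 7.2.4 lists an interval history and an adverse event enquiry, plus medications and reasons for leaving when the exit is premature. It has no pregnancy item. The last scheduled pregnancy test is at Visit 21.

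**The concern.** The definition of a treatment-emergent SAE assumes the same 30 days of observation after the last dose for everyone. The visit that should close that interval is counted from randomisation, and its window is independent of the Visit 21 window. The time from last dose to final enquiry therefore depends on where two visits happen to fall, and the nominal schedule stops slightly short.

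Tolerability and toxicity form the stated secondary objective, and the SAP tabulates treatment-emergent SAEs by arm. If the last enquiry comes before the interval closes, later events enter the tables only when someone volunteers them. Pregnancy has the weaker cover: the last test is at Visit 21 and the final call has no item for it, although reporting runs for 30 more days.

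**Working it through.** The check is calendar arithmetic.

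**Inputs.** Month = 28 days; Visit 21 = day 504 ±14; Visit 22 = day 532 ±10 (Summary Table; Sections 7.2.3.1 and 7.2.4). Windows after the last dose: 7 days for non-serious events and 30 days for SAEs (Section 8.1.1.1), and 30 days for pregnancy (Section 8.3.4).

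**Plan's own figures.** 18 × 28 = 504 and 19 × 28 = 532, so both nominal days reproduce exactly. The synopsis promises one month of follow-up after drug therapy; in the table's months that is 28 days, not 30.

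**Permitted days.** Visit 21: 504 − 14 = 490 to 504 + 14 = 518. Visit 22: 532 − 10 = 522 to 532 + 10 = 542.

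**Gap from last dose to call**, assuming dosing continues to Visit 21:

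- On schedule: 532 − 504 = 28 days. The 30-day window closes on day 534, so the shortfall is 2 days.
- Shortest: 522 − 518 = 4 days, which is also inside the 7-day window for non-serious events.
- Longest: 542 − 490 = 52 days.

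| Last dose (day) | 30-day window closes | Gap if call on day 522 / 532 / 542 |
|---|---|---|
| 490 | 520 | 32 / 42 / 52 |
| 502 | 532 | 20 / 30 / 40 |
| 504 | 534 | 18 / 28 / 38 |
| 512 | 542 | 10 / 20 / 30 |
| 518 | 548 | 4 / 14 / 24 |

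A call on day 532 reaches 30 days only if the last dose was on or before day 502 (532 − 30). After day 512 (542 − 30), no call within the Visit 22 window reaches 30 days, however carefully the site follows the schedule.

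**Spread.** There are 29 × 21 = 609 in-window pairs of days. Of these, 336 (55%) give fewer than 30 days and 6 (1%) fewer than 7. This counts pairs; it is not a probability, because visit dates are not uniform over their windows.

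**Early leavers.** Section 7.2.4 counts from complete withdrawal, and the table footnote from early termination or withdrawal; neither is the last dose. Section 7.2.5 also sends participants who stop all study drugs but stay in follow-up to the Section 7.2.4 contact, whose clock starts at an event that has not happened for them.

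**The case against.** The strongest reply is that the mismatch is small and that reporting does not depend on visits. On schedule 2 days are missed, about 0.4% of a treatment-emergent period of 534 days (2/534), and even the extreme case misses 26 of 548 (5%). The +10 side of the window allows a compliant call on day 534 or later. Section 8.3.2 asks participants and those close to them to report hospitalisation, serious changes in health or death at once. Section 8.3.4 makes pregnancy reportable whatever the visit schedule, and Section 8.3.5 covers later SAEs attributed to study drug. The schedule is the same in both blinded arms. All of this stands. What it leaves open is scheduled enquiry, which Section 8.3 requires to be consistent across evaluation time points.

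Three stronger readings are tempting, and the documents do not support them:

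- **That Visit 22 is the only later contact for people who stop treatment early, so that their follow-up is the shortest.** Those who stop all drugs are asked back at months 12 and 18 (Sections 5.3.3 and 7.2.5). Section 8.3.1 requires enquiry at each visit about events since the previous one, so a later visit looks back over the whole window. Those who stop only pirfenidone or placebo keep the full schedule.
- **That an exit call one day after stopping would comply.** Taken alone, the 30-day limit is an upper bound, but the ±10 days attached to it makes sense only around a target, which suggests days 20 to 40. The wording is ambiguous and does not establish one-day coverage.
- **That a 4-day gap is typical.** It needs dosing up to a Visit 21 on its last permitted day and a call on the first permitted day.

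**Conclusion.** The mismatch is real and modest. For completers, the only scheduled safety contact after treatment, apart from voluntary annual follow-up, is not tied to the last dose. It falls 2 days short on schedule, and for a last dose after day 512 it cannot reach 30 days within its window. The larger problem is the spread of 4 to 52 days rather than the nominal shortfall. For early leavers the timing needs clarifying, mainly for those who withdraw completely or do not return at months 12 and 18.

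The 4-to-52-day range assumes that dosing continues to Visit 21. The documents say that therapy is completed at month 18 but give no stop day when Visit 21 is early or late. Section 7.2.3.1 lists dispensing at Visit 21 while the summary table does not mark it; those two places must be reconciled. A last dose before Visit 21 lengthens the gap, and one after it shortens the gap. The range also sets aside the emergency extension of visit windows in Section 17.5.

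A reader might infer that late events are lost or that the comparison between arms is biased. Neither is shown: passive reporting remains, and the timing rule is common to both arms. The primary endpoint is unaffected.

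**What to change.** - In Section 7.2.4, the visit tables and the exit-visit footnote, time the existing final or exit phone contact from the actual last dose of the last study drug stopped, no earlier than 30 days after it (for example, a window of +10 days with no minus side).
- Add a pregnancy question to the adverse event enquiry at that contact.
- Leave the recording periods in Sections 8.3.1 and 8.3.2 as they are. Ending them at the re-timed call would look tidy, but it would cut off SAE recording for participants who stop drug early and stay in follow-up.
- The SAP reports that enrolment stopped early. For participants who have already finished, report the actual interval from last dose to last safety contact by arm, including how many had fewer than 30 days.

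Cost: protocol wording and one added question, with no new visit. A call at exactly 30 days would come 2 days after the present day 532 for a last dose on day 504 (534 − 532) and 16 days after it for a last dose on day 518 (548 − 532). At the middle of a +10-day window (35 days after the last dose), the delays are 7 and 21 days. For most completers the call moves by a few days, and by about two to three weeks when the last dose is late.
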